8. ADVERSE EVENTS (AE) AND SERIOUS ADVERSE EVENTS (SAE)

The investigator is responsible for the detection and documentation of events meeting the criteria and definition of an AE or SAE. During the study, in case of a safety evaluation, the investigator or site staff will be responsible for reporting AEs and SAEs, as detailed in this section of the protocol.

During the screening period, only adverse event related to the screening procedures will be collected. Adverse events related to the antiretroviral treatments will be reported directly to the concerned pharmaceutical company according to the local process.

Any disease progression will not be reported in the eCRF as an adverse event, but will be documented in the efficacy section.

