8.1. Definition of an AE

Any untoward medical occurrence in a subject or clinical investigation subject administered a pharmaceutical product and which does not necessarily have to have a causal relationship with this treatment.

An AE can therefore be any unfavorable and unintended sign (including an abnormal laboratory finding), symptom, or disease (new or exacerbated) temporally associated with the use of a medicinal product, whether or not considered related to the medicinal product.

Note: The official definition also extends to AEs occurring in the placebo arm. Because of regulatory requirements, events occurring during pre-and post-treatment periods will also be designated as AEs. Therefore, reporting of such events, AEs and SAEs, will commence when the subject is enrolled into the study (date of signature of the informed consent) up until 4 weeks after the end of the treatment visits. The period after discontinuing study drug may be extended if there is a strong suspicion that the drug has not yet been eliminated.

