8.4. Time Period, and Frequency of Detecting AEs and SAEs

All AEs and SAEs occurring from the time a subject consents to participate in the study until 4 weeks after he or she has completed or discontinued the investigational product must be recorded in the subject's eCRF. Importantly, SAEs will have to be reported to ABIVAX or its designee within 24 hours of awareness of an SAE.

Legislative guidance requires also reporting any **related** SAEs to be reported after the subject finished the study if the investigator becomes aware of them.

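### Protocol section 8 bars disease progression from being recorded as an adverse event, contradicting sections 8.1, 8.4, 8.3.1 and 5.4.1, so a clinical HIV-related event could be missing from the safety tables

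*Protocol*

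**What the plan says.** Protocol section 8, before its numbered subsections, states: "Any disease progression will not be reported in the eCRF as an adverse event, but will be documented in the efficacy section". Neither document defines disease progression.

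The preceding paragraph of section 8 contains two further rules. The first is: "During the screening period, only adverse event related to the screening procedures will be collected". Soon after it comes: "Adverse events related to the antiretroviral treatments will be reported directly to the concerned pharmaceutical company according to the local process".

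Other parts of the protocol set a wider rule:

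- Section 8.1 includes in the definition of an adverse event any "symptom, or disease (new or exacerbated) temporally associated with the use of a medicinal product, whether or not considered related to the medicinal product".
- Section 8.4 covers "All AEs and SAEs occurring from the time a subject consents to participate in the study" up to four weeks after study drug, and these "must be recorded in the subject's eCRF". It states no exception.
- Section 8.3.1 exempts clinically significant findings of the disease under study only when they were present at the start and have not worsened.
- Section 5.4.1 requires new clinically relevant findings since baseline to be documented as adverse events.
- Section 8.5 asks, for each recorded event, whether the study product may have caused it. Underlying disease and concomitant medication are weighed as alternative causes.

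The SAP has no matching exclusion. Section 11.4.1 summarises treatment-emergent and serious events and lists the adverse events recorded on the CRF.

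**The concern.** The progression sentence and the general rules give opposite instructions for the same event. One site, or one investigator on different days, could record an HIV-related illness as an adverse event or leave it out, and each choice would be defensible from the text.

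This bears on a stated objective. Safety of ABX464 in combination with antiretrovirals is a secondary objective (protocol 2.2), and the number and grade of treatment-emergent adverse events is the secondary endpoint that serves it (5.2). ABX464 is added to continuing antiretroviral therapy, so clinical worsening of HIV disease is an outcome that the safety record should be able to show. An event that never becomes an adverse-event record receives no grade, no seriousness classification and no assessment of causality to ABX464. It also cannot be a dose-limiting toxicity, because section 3.1.2 defines that as an adverse event of grade 3 or higher.

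**Working it through.** No power or sample-size figure is involved. The check is a comparison of passages, followed by a small illustration.

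**1. One event under each rule.** Suppose an HIV-infected subject on ABX464 develops a new HIV-related illness that the investigator regards as progression.

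- Section 8 opening: not an adverse event in the eCRF.
- Section 8.1: an adverse event, because it is new disease, related or not.
- Section 8.4: must be in the eCRF.
- Section 8.3.1: abnormal findings that are clinically significant and have worsened are reportable.
- Section 5.4.1: a new clinically relevant examination finding is an adverse event.
- Sections 8.2 and 8.2.1: if the subject is hospitalised, the event is serious. Progression is not among the listed hospitalisations that need no SAE report.

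The first rule cannot be met together with the others. Section 8.6 routes serious reports through eCRF forms, so the handling of serious progression is also unclear.

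**2. Where an excluded event would go.** Section 8 sends it to the efficacy section. Protocol 5.2 and SAP 11.3.2 contain these HIV-related endpoints: rectal-tissue reservoir, total viral DNA, HIV-1 RNA, and CD4+ and CD8+ counts. All are laboratory measures, summarised on the FAS. Viral load and CD4+/CD8+ counts are scheduled at baseline, Day 28, end of treatment and both follow-up visits (protocol 5.3). Virological loss of control therefore has an analysis. A clinical HIV-related illness has none: there is no progression endpoint, definition or table in protocol 5.2 or 9.2 or in SAP 11.3. SAP 10.1 would at most put it in a data listing, if the eCRF captured it.

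**3. Antiretroviral-attributed events.** The sentence names a route to the manufacturer. It does not say whether the event is also recorded in the eCRF. It follows a rule about the screening period, so it may apply only there. Sections 8.4 and 8.5 favour recording. The text is ambiguous, and it becomes a contradiction only if direct reporting replaces eCRF recording.

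**4. Size, for illustration.** Inputs are the cohort sizes in protocol 3.1.1 and the total in 9.4.

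- HIV-infected subjects: 12 (Cohort 1) + 12 (Cohort 3) = 24. Adding 12 (Cohort 2) gives 36, as stated. 24/36 = 66.7%.
- Assume one true event in a cohort of 12: 1/12 = 8.3% (exact 95% interval 0.2% to 38.5%). If it is omitted: 0/12 = 0% (0% to 26.5%).
- Over both HIV-infected cohorts: 1/24 = 4.2% (0.1% to 21.1%). If it is omitted: 0/24 = 0% (0% to 14.2%).

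The intervals are Clopper-Pearson. The documents give no rate for such events, so these figures show only what one omission would do.

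**The case against.** The strongest reply is that the trial already captures what matters. A reader might infer from section 8 that loss of HIV control could vanish from the study. The documents do not support that: the synopsis lists virological control under efficacy, protocol 5.2 and the SAP summarise viral load, cell counts and reservoir measures, and the Cohort 1 interim analysis includes viral load, cell counts and total HIV-1 DNA. This part of the reply stands in full.

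A reader might also infer that section 8 removes antiretroviral toxicity, or an interaction with ABX464, from the eCRF. It does not say so. An investigator who suspects an interaction would answer yes to the causality question in 8.5 and record the event, and SAP 11.4.1 counts missing relatedness as drug-related. This stands as a reason to call the sentence ambiguous. It does not remove the need to clarify it, because both safeguards work only on events that have been recorded.

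The dose-limiting-toxicity consequence is narrow. The stopping count covers the first four treated subjects and needs a probable or definite relation to treatment, and an event judged so is unlikely to be called mere progression. That reduces the likelihood but does not make the rule coherent.

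Finally, subjects are virologically suppressed, have CD4+ counts of at least 600 per mm³ at screening, stay on antiretrovirals and are treated for 28 or 84 days. Clinical progression may well be rare. That limits the expected loss. It does not resolve the contradiction, since none of these points tells a site which instruction to follow.

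**Conclusion.** Wrong as written: the progression exclusion in protocol section 8 contradicts sections 8.1, 8.4, 8.3.1 and 5.4.1. What can be lost is a clinical HIV-related event classed as progression, together with its grade, seriousness and causality, from the treatment-emergent and serious adverse-event summaries and from dose-limiting-toxicity eligibility. The antiretroviral sentence is a separate and lesser ambiguity.

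The size cannot be estimated. The 24 of 36 counts HIV-infected subjects, not subjects affected, and the 8.3 points is simply 1/12, which would apply to any missed event in any cohort of that size. A reader might add that the exclusion spoils the comparison of adverse-event rates with the uninfected cohort. That argument carries little weight here: the cohorts are not randomised, already differ in HIV status, dose or duration, and are summarised only descriptively.

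The conclusion rests on reading the progression sentence as it stands, without qualification. The eCRF pages are not among the documents, so it is not known whether they offer a field for progression.

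**What to change.** Reconcile the opening of protocol section 8 with 5.4.1, 8.1, 8.3.1, 8.4 and 8.5:

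1. Delete the progression exclusion, or limit it to the laboratory endpoints already analysed (HIV-1 RNA, CD4+/CD8+ counts, reservoir measures), so that clinical HIV-related worsening is recorded as an adverse event. If it is limited, put the same exception in 8.3.1 and 8.4 so that the sections agree.
2. State that notifying the antiretroviral manufacturer is in addition to eCRF recording, with causality to ABX464 assessed for each event, and say whether that sentence applies beyond screening.
3. In the same edit, align the screening-period rule in section 8 with the start of recording at consent in 8.1 and 8.4.

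The SAP needs no structural change, because recorded events then enter the tables of section 11.4.1. One confirming line there would help. SAP section 8 describes the Cohort 1 interim analysis as already produced, so Cohort 1 source records should be checked for events handled under the present wording.

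The cost is protocol wording, a line in the eCRF instructions and a few more adverse-event records. Adverse-event counts may become slightly less favourable.

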8.1. Definition of an AE

Any untoward medical occurrence in a subject or clinical investigation subject administered a pharmaceutical product and which does not necessarily have to have a causal relationship with this treatment.

An AE can therefore be any unfavorable and unintended sign (including an abnormal laboratory finding), symptom, or disease (new or exacerbated) temporally associated with the use of a medicinal product, whether or not considered related to the medicinal product.

Note: The official definition also extends to AEs occurring in the placebo arm. Because of regulatory requirements, events occurring during pre-and post-treatment periods will also be designated as AEs. Therefore, reporting of such events, AEs and SAEs, will commence when the subject is enrolled into the study (date of signature of the informed consent) up until 4 weeks after the end of the treatment visits. The period after discontinuing study drug may be extended if there is a strong suspicion that the drug has not yet been eliminated.

8.2. Definition of a SAE

A serious adverse event (experience) or reaction is any untoward medical occurrence that, at any dose:

- a) Results in death

NOTE: Death is an outcome of an AE, and not an AE in itself. Event which led to death should be recorded with fatal outcome.

- b) Is life-threatening

NOTE: The term 'life-threatening' in the definition of 'serious' refers to an event in which the subject was at risk of death at the time of the event. It does not refer to an event, which hypothetically might have caused death, if it were more severe.

- c) Requires hospitalization or prolongation of existing hospitalization

NOTE: In general, hospitalization means that the subject has been detained (usually involving at least an overnight stay) at the hospital or emergency ward for observation and/or treatment that would not have been appropriate in the physician's office or out-patient setting. Complications that occur during hospitalization are AEs. If a complication prolongs hospitalization or fulfills any other serious criteria, the event is serious. When in doubt as to whether "hospitalization" occurred, or was necessary, the AE should be considered serious.

Hospitalization for elective treatment of a pre-existing condition that did not worsen after informed consent was given is not considered an AE.

- d) Results in persistent or significant disability/incapacity,

NOTE: The term disability means a substantial disruption of a person's ability to conduct normal life functions. This definition is not intended to include experiences of relatively minor medical significance such as uncomplicated headache, nausea, vomiting, diarrhea, influenza, and accidental trauma (e.g. sprained ankle) which may interfere or prevent everyday life functions but do not constitute a substantial disruption.

- e) Is a congenital anomaly/birth defect

- f) Is another medically important condition: This refers to an AE that may not be immediately life-threatening or results in death or hospitalization but may jeopardize the subject or may require intervention to prevent

one of the outcomes listed above. Based on medical and scientific judgment this should usually be considered serious.

If there is any doubt about whether or not an AE is serious, the investigator should contact the sponsor.

8.2.1. Events and/or Outcomes Not Qualifying as SAEs

Any hospitalization, or prolongation of hospitalization due to the circumstances listed below, will not be reported as SAE:

- Planned medical/surgical procedure;
- Planned medical/surgical admission (planned prior to entry into study, appropriate documentation required), for the disease under study;
- Administrative or social reasons (e.g. lack of housing, economic inadequacy, care-giver respite, family circumstances).

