5.4.6. Rectal Biopsy/ Flexible sigmoidoscopy

Flexible sigmoidoscopy is routinely utilized in gastrointestinal and HIV research clinical trials. Based on data from more than 1,000 procedures. Flexible sigmoidoscopy with up to 20 biopsies taken using jumbo forceps has shown a low adverse event rate, even when performed repeatedly in clinical trial participants.

At baseline (Day 1), at Day 28, at Day 56 (only for cohort 1&3) and at Day 84/Day 112 (only for cohort 3) a flexible sigmoidoscope will be inserted into the rectum of the subjects to 15 cm from the anal margin, where 15 to 20 biopsies will be collected for flow cytometry, ex vivo tissue infectivity assays, and PK.

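### Protocol 8.2.1 exempts a hospital stay for any planned procedure from SAE reporting, with no limit on when or why it was planned, which conflicts with the narrower exemption in 8.2(c)

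*Protocol*

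**What the plan says.** Protocol section 8.2 lists the criteria that make an event serious. Criterion (c) is "Requires hospitalization or prolongation of existing hospitalization". The note to (c) has two rules that matter here.

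- An exemption: "Hospitalization for elective treatment of a pre-existing condition that did not worsen after informed consent was given is not considered an AE".
- A rule on complications: "If a complication prolongs hospitalization or fulfills any other serious criteria, the event is serious".

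Section 8.2.1 then lists circumstances that do not qualify. Its lead-in is categorical and covers prolonged stays as well as admissions: "Any hospitalization, or prolongation of hospitalization due to the circumstances listed below, will not be reported as SAE". The first two bullets are:

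- "Planned medical/surgical procedure", with nothing further.
- "Planned medical/surgical admission (planned prior to entry into study, appropriate documentation required), for the disease under study".

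The third bullet covers administrative and social reasons and is not at issue. Section 8.2.1 does not refer back to the exemption or the complication rule in 8.2(c).

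**The concern.** Section 8.2(c) ties its exemption to the condition being treated: it must predate consent and must not have worsened. The first bullet of 8.2.1 ties its exemption only to the procedure being planned. Most non-emergency procedures are planned in that sense, including those arranged during the trial for a problem that arose during the trial. The second bullet shows that the drafters knew how to add limits on timing, documentation and indication, and the first bullet has none of them. An investigator who follows 8.2.1 literally can therefore mark as non-serious an event that 8.2(c) makes serious.

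The classification has consequences. Serious treatment-emergent events are part of a secondary endpoint (Protocol 5.2, SAP 4.2). SAE status is what starts the 24-hour report of an adverse event to the sponsor (Protocol 8.4 and 8.6), and that report feeds the sponsor's duties to authorities (8.7).

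**Working it through.** The plan states no figure on this point and no arithmetic applies. The check sets the two sections side by side for each type of hospital stay.

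| Reason for the stay | Under 8.2(c) | Under 8.2.1, first bullet | Result |
|---|---|---|---|
| Elective procedure for a pre-existing condition, not worsened since consent | Not an AE | Not an SAE | Agree |
| Unplanned admission for a new event | SAE | Does not apply | Agree |
| Procedure scheduled on study for a condition that arose after consent | SAE | Exempt | Conflict |
| Procedure scheduled on study for a pre-existing condition that worsened after consent | SAE | Exempt | Conflict |
| Stay prolonged by a complication of a planned procedure | Serious | Depends on how far "due to" extends | Unclear |

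The third and fourth rows need no strained reading. The procedure is planned, the stay is due to it, and the lead-in says that it is not reported.

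Next, what happens to an event in those two rows if the investigator enters seriousness as no:

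1. **Other criteria.** Section 8.2.1 exempts hospitalisations. It does not cancel the other criteria in 8.2, such as death, threat to life, disability or medical importance. Only an event that is serious through (c) alone is exposed.
2. **Recording.** The event is still entered in the eCRF as an AE (8.4) and graded (8.5).
3. **Reporting.** The 24-hour rule in 8.4 and 8.6 applies to SAEs, so it is not triggered.
4. **Tables.** SAP 11.4.1 counts a serious TEAE where seriousness is yes or missing. An entry of no drops out of those tables and out of the row for any serious adverse event. The SAP describes no later review of seriousness. If the event starts after End of Rx, the SAP classes it as post-treatment-emergent, and only the row for any serious adverse event is affected.

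**The case against.** The strongest reply is that this is loose wording in a standard exemption list, with several safeguards around it. Criterion (f) covers events that may need intervention to prevent a listed outcome and says they should usually be treated as serious, so it would catch many of the exposed events. Section 8.2 tells the investigator to contact the sponsor when in doubt. The dose-limiting-toxicity and grade 4 rules (3.1.2) depend on grade and causality and not on the SAE flag. The DSMB reviews safety after every four patients recruited (3.1.3), and events of grade 3 or higher are tabulated separately. All of this stands and limits the harm. It does not remove the conflict: advice for cases of doubt does not help an investigator who reads a definite exclusion and has no doubt.

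A reader might go further and infer that complications of the study's own biopsies are exempt, because each sigmoidoscopy is a planned procedure "where 15 to 20 biopsies will be collected for flow cytometry" and other assays. The documents do not support that as the main reading. A stay due to a planned procedure most naturally means the stay that the procedure itself needs. No admission is planned for sigmoidoscopy, and 8.2(c) already says that a complication prolonging a stay is serious. The point is worth a clarifying clause and no more.

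For the same reason, a count of procedures does not measure the defect. The section 5.3 schedule gives 12 x 3 + 12 x 2 + 12 x 4 = 108 sigmoidoscopies. Section 5.4.6, read literally, adds one at Day 56 in Cohort 3, giving 108 + 12 = 120; the two sections need reconciling separately. Either figure counts exposure and not misclassified events. The share of a cohort that one subject represents, 1/12 or 8.3%, is no measure of it either.

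**Conclusion.** The conflict is real. For an admission to carry out a procedure scheduled on study for a new or worsened condition, 8.2(c) says SAE and 8.2.1 says not. This is a contradiction between two rules and not a missing detail.

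Its reach is narrow. What can be lost is the SAE flag, the 24-hour report and the entry in the serious-event tables, and only for events that meet no criterion other than hospitalisation. The AE itself is not lost. The documents give no rate for such admissions, so the number cannot be estimated. With 36 subjects, each followed for at most about 140 days, few are likely.

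A reader might also infer that one missed SAE would change the safety conclusion. The documents do not support that: the safety analysis is descriptive and no decision rule uses a count of SAEs.

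The conclusion assumes that investigators apply the first bullet as worded. If the site already reads it in the light of 8.2(c), the correction only writes down current practice.

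**What to change.** Reconcile sections 8.2 and 8.2.1 of the protocol.

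- Limit the first bullet of 8.2.1 to procedures planned before informed consent for a pre-existing condition that has not worsened. An elective procedure arranged later for an unworsened pre-existing condition stays outside SAE reporting anyway, because 8.2(c) says it is not an AE.
- Add that 8.2.1 does not override 8.2(c): a complication that requires or prolongs hospitalisation is serious, including a complication of a study sigmoidoscopy or biopsy.

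The cost is about two sentences of protocol text and possibly one or two more SAE reports. Design, sample size and analysis do not change, and the SAP needs no edit because it takes the seriousness flag as recorded.
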